This study will evaluate the feasibility, safety, and efficacy of intradermal vaccination of prostate cancer patients with alpha-type-1-polarized dendritic cells (α DC1) loaded with apoptotic allogeneic tumor (LNCap). The study will target men with recurrent prostate cancer, who failed local therapy, have no measurable metastasis, but have a rising PSA with a doubling time of less than 10 months. The selection of this study group enables us to evaluate **time to PSA progression**, a highly relevant, **clinical primary endpoint of efficacy in this two arm study**. In order to facilitate infiltration of vaccination-induced T cells into tumor site(s) and to reduce tumor-specific tolerance, **subjects will receive the vaccine in combination with limited androgen ablation (AA)** with a LHRH analogue for 3 months. Subjects will be randomly assigned to one of two cohorts. In cohort A subjects will be first treated with limited AA alone for 3 months, and at the time of PSA relapse ($\text{PSA} \geq 1 \text{ ng/dL}$) will receive the DC vaccine in conjunction with AA. In cohort B, the sequence of treatment will be reversed. Efficacy will be estimated as the within-subject difference in time to PSA relapse following the combination treatment as compared to the AA alone, thus, each subject will serve as his own control. All subjects will commence the α DC1-based vaccination 2 weeks prior to treatment with the LHRH analogue. Each subject will receive 1 *intradermal (i.d.)* dose of the vaccine at weeks 1, 5, 9, and 13 for a total of 4 doses. Additional courses of vaccination may be administered to subjects without evidence of disease progression every 3 months (± 1 month) for up to 12 months depending on the number of doses originally produced and available after the 4 intended protocol doses. All doses of the vaccine will be administered intradermally (*i.d.*).

STUDY DESIGN

VACCINE SCHEMA

Lupron 22.5 mg i.m. or Zoladex 10.8 mg s.c.
 The LHRH analogue will be administered 2 weeks after the 1st dose of the vaccine.

Study cohorts:

- **Cohort A:**
LHRH analogue or limited androgen ablation (AA) followed by Vaccine + AA at time of PSA relapse
- **Cohort B:**
Vaccine + AA followed by AA at time of PSA relapse

^a Vaccine injections may be delivered on a ± 2 workday schedule.

1 OBJECTIVES

Dendritic Cell (DC)-based vaccination is a new treatment option for cancer patients. While the previous DC-based vaccination trials have shown the safety of this approach and its ability to induce objective clinical responses, the overall efficacy of DC-based vaccines is still disappointing (Rosenberg et al., 2004). Our preliminary in vitro data indicate that type-1-polarized DC (α DC1) are 40-fold more potent than the current “gold standard” of clinically-applied DC (sDC) in their ability to induce tumor-specific CTLs (see Appendix I for the Summary of the Preclinical Data and the Protocol and Appendix II for our original publication describing CDC1 (Mailliard et al., 2004)). Thus this trial will enroll subjects with prostate cancer who have failed local therapy and present with PSA-only disease. At the time of study entry, subjects must have a PSA doubling time of less than 10 months and an absolute PSA level of > 2.0 ng/mL. This is a two-arm study, whereby subjects will either be randomized to limited androgen ablation (AA) for 3 months followed by the DC vaccine + AA at the time of PSA relapse (PSA > 1 ng/dL) or the converse sequence of treatment. Thus all subjects will be treated with both AA as well as AA + vaccine, with each subject, in essence, serving as his own control, in estimating the time to PSA recovery following limited AA. The α DC1 vaccine will be administered every 4 weeks x 4 and then, if vaccine is available from the original production, every 3 months (± 1 month) in subjects who continue to respond.

1.1 Primary Objectives

- Feasibility objective: the ability to successfully generate and administer the alpha-DC1 vaccine.
- Safety objective: assess the tolerability and toxicity of the alpha-DC1 vaccine.
- Efficacy objective: evaluate the effect of the alpha-DC1 vaccine on time to PSA progression compared to AA alone. PSA progression is defined as a rise in the PSA value to ≥ 1.0 ng/mL.

1.2 Secondary Objectives

- To determine the change in PSA velocity prior to and following the proposed treatment.
- To evaluate (in all subjects) the vaccination-induced DTH responses to LNCap, the cell line vaccine, and to compare this with vaccination-induced responses to tumor-untreated antigen (KLH).
- To evaluate the vaccination-induced changes of Th1/Th2 profiles of the responses to PAP and PSMA.
- To evaluate the CTL responses in blood to the whole LNCap cells (in all subjects) and (in all subjects who are HLA-A2 positive) the CTL responses to HLA-A2.1 restricted peptides derived from PAP and PSMA.
- To comprehensively evaluate the CD4⁺ and CD8⁺ T cell responses (fine specificity and Th1/Th2/T_{reg} cytokine profile) to the previously-identified and novel immunogenic epitopes of PAP and PSMA, using the EPIMAX system.

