4 SUBJECT SELECTION

4.1 Eligibility Criteria

- Patients with histologically proven prostate cancer and tumors limited to the prostate (including seminal vesicle involvement, provided all visible disease was surgically removed) who have completed local therapy and have an elevated PSA after surgery or rising PSA after radiation therapy, as defined below.
- Age 18 years or older
- Histologically confirmed diagnosis of prostate cancer.
- Previous treatment with definitive surgery or radiation therapy or both.

- No evidence of metastatic disease on physical exam, CT/MRI/CXR (see Section 7.1 for radiologic imaging), and bone scan within 4 weeks prior to randomization.
- Prior neoadjuvant/adjuvant hormonal, androgen deprivation therapy, or chemotherapy is allowed if it was last used > 12 months prior to first vaccination.
- No therapy modulating testosterone levels (such as leuteinizing-hormone releasing-hormone agonists/antagonists and antiandrogens) is permitted within 12 months prior to first vaccination. Agents such as 5 α -reductase inhibitors, ketoconazole, megestrol acetate, systemic steroids (replacement doses of steroids are allowed), PC-SPEs, and Saw Palmetto are not permitted at any time during the period that the PSA values are being collected.
- Hormone-sensitive prostate cancer as evident by a serum total testosterone level > 150 ng/dL or > 6 nmol/L at the time of enrollment within 4 weeks prior to randomization.
- All patients must have evidence of biochemical progression as determined by a reference PSA value followed by 1 confirmatory rising PSA value, higher than the previous value, obtained at least 2 weeks apart. All of these PSA values must be obtained at the same reference lab, and all must be done within 6 months prior to enrollment.
- The most recent of the PSA values must be \geq 2.0 ng/mL. This measurement must be obtained within 1 month prior to enrollment.
- The PSA doubling time (PSA-DT) must be less than 12 months.
- ECOG performance status 0 or 1.
- Patients must have normal organ and marrow function as defined below:
 - Absolute neutrophil count > 1,500/ μ L
 - Platelets > 100,000/ μ L
 - Total bilirubin 1.5 x upper limit of normal (ULN)
 - SGOT (AST) and SGPT (ALT) < 2.5 x institutional ULN
 - Creatinine 1.5 x ULN

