8.3 Evaluation of Clinical Responses

The primary clinical endpoint is the time to PSA progression. Since all subjects will be treated with androgen ablation for 3 months, the expectation is that at the outset all subjects will have undetectable PSA levels. As subjects recover their testosterone levels (in 3 to 6 months), they are expected to develop a PSA relapse (5 to 7 months).

Thus time to progression (TTP) will be defined as time from starting of androgen ablation (week 2) to time of either developing *PSA progression* (see below) or the development of metastatic disease (whichever occurs sooner). Typically PSA progression will precede the development of metastatic disease.

Progressive Disease: All subjects are expected to have a PSA < 0.1 following androgen ablation. Thus PSA progression will be defined as a PSA rise of at least 1.0 ng/dL, measured at least twice, with the two values being at least 1 month apart. Changes in PSA below 1.0 ng/dL will be evaluated for the PSA slope and PSADT.

PSA Slope: The change in PSA will be graphically depicted and a PSA slope calculated. The change in PSA slope (and PSADT) pre-treatment, during treatment, and off-treatment will be determined to see if vaccine therapy has any disease modifying effects, over and above castration. This end-point is exploratory, but may lead to continued interest in this agent if the PSA slope (or PSADT) is decreased during treatment.

Clinical Progression: The appearance of new lesions on examination or radiographs (CT scan or

bone scan), or development of symptoms consistent with metastatic disease (i.e. bone pain).

Identification of Lesions: All measurements should be taken and recorded in metric notation. All baseline evaluations should be performed as closely as possible to the beginning of treatment and never more than 4 weeks before randomization. A sum of the longest diameter (LD) for all target lesions will be calculated and reported as the sum LD. The sum LD is used as reference to assess progression.

Clinical Progression free survival: This is the interval from entry to study to date of first documented lesion.

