9.5 Data Analysis

Subjects will be required to have monthly PSA monitoring. This will enable linear interpolation between PSA samples to detect the time at which PSA progression occurs following each course of therapy. The efficacy endpoint is estimated by the difference between time to PSA progression for the AA+DCV arm and the AA arm. This difference will be tested for significance with a one tailed signed rank test. Other conventional estimates of clinical efficacy will also be calculated including PSA doubling time and PSA velocity. The PSA-DT will be calculated as follows:

The logarithm of a minimum of two PSA measurements will be plotted against the time of each PSA measurement. If 3 or more measurements are available a linear regression equation will be estimated. Two sequential PSA measurements (actual or estimated by linear regression) will be denoted as PSA1 and PSA2. Denote their times of blood samples as t1 and t2, respectively. Thus the PSA doubling time is: $\log(2)[t2 - t1] / [\log(\text{PSA}2) - \log(\text{PSA}1)]$.

Further analysis will involve testing the immunologic response of subjects receiving the α DC1-based vaccine. The principal measure of improved immunogenicity will be the comparison of pre to post α DC1-based vaccine T cell response to prostatic acid phosphatase (PAP) as measured by the IFN- γ Elispot assay. We expect that prostate cancer subjects undergoing androgen ablation in the absence of immune stimulation will have a negative or very low Elispot count for measuring reaction to PAP. Even with a nominal count of 5 spots in the group, a sample of 7 subjects with androgen ablation alone and 7 subjects treated with androgen ablation + α DC1-based vaccine will provide 90% power to detect a difference of double the Elispot count (average of 5 to 10 spots) using a one tailed alpha level Wilcoxon test if the Elispot counts have a Poisson distribution. Additional immunologic testing will be conducted by analyzing subject profiles before treatment and after each course of therapy. Immunologic endpoints include T cell reactivity by IFN γ or IL-5 Elispot, cytokine release assays for cytotoxicity and DTH tests (as measured by induration in mm). Changes over time will be tested with the Friedman Test or, if there are missing values, the Mack-Skillings procedure.

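### Before-to-after PSA velocity cannot show a vaccine effect: entry PSA is at least 2.0 ng/mL, the post-ablation rise runs from about 0.1 to 1.0, and velocity scales with PSA level

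*Combined protocol and SAP*

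**What the plan says.** Section 1.2, and Section 8.1 in the same terms, list as a secondary efficacy objective: "To determine the change in PSA velocity prior to and following the proposed treatment". Neither gives a formula, a scale, a sampling window or a test.

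Section 8.3 speaks of slope and doubling time together. Its progression paragraph says: "Changes in PSA below 1.0 ng/dL will be evaluated for the PSA slope and PSADT" (the unit is printed as ng/dL; I read it as ng/mL, as in Sections 1.1 and 8.1). Its slope paragraph says: "The change in PSA slope (and PSADT) pre-treatment, during treatment, and off-treatment will be determined", with the aim of finding a disease-modifying effect beyond castration. It does not say whether the slope is on the raw or the log scale. It adds "This end-point is exploratory", and says interest in the agent may continue "if the PSA slope (or PSADT) is decreased during treatment".

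Section 9.5 lists both measures: "Other conventional estimates of clinical efficacy will also be calculated including PSA doubling time and PSA velocity". The only formula that follows is for doubling time, on the log scale: "The logarithm of a minimum of two PSA measurements will be plotted against the time of each PSA measurement".

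Section 4.1 fixes the entry level: "The most recent of the PSA values must be" at least 2.0 ng/mL. It needs a reference value and one higher value, at least 2 weeks apart and within 6 months before enrollment.

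**The concern.** For exponential growth, velocity equals PSA level times growth rate. A velocity read at or near entry is taken at a PSA of 2 or more. A velocity read during the rise after AA is taken between about 0.1 and 1.0. The before-to-after change therefore mixes growth rate with the PSA level at which it was read, and the level part always points towards improvement. Section 8.3 proposes to read a slope change as possible disease modification, so this artefact could be reported as a vaccine benefit.

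Velocity and doubling time can also point in opposite directions for the same man, and no section says which one decides. Two further inconsistencies make this worse. The endpoint is secondary in 1.2 and 8.1 but exploratory in 8.3. And 8.3 counts a decreased PSADT as favourable, although a shorter doubling time means faster growth.

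**Working it through.** The plan states no power, threshold or expected value for PSA kinetics, so there is no figure to reproduce for this endpoint.

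**Inputs from the documents.** Entry PSA P is at least 2.0 ng/mL (4.1). Entry doubling time D is below 12 months (4.1) or below 10 months (Section 1); I use 3, 6 and 10. PSA is expected below 0.1 after AA (8.3; 0.1 used). Progression is at 1.0 ng/mL (1.1). Median time to progression is 6 months, 90% between 5 and 7, after 3 months of AA (Section 5).

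**Assumption.** The rise from 0.1 to 1.0 takes W months. W = 3 is the 6-month median less the 3 months of AA; the 5-7 month spread gives W = 2 to 4.

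**Formulas.**
- Pre-treatment velocity, short sampling gap: P × ln2 / D.
- Pre-treatment velocity, values 6 months apart (the longest gap 4.1 allows): P × (1 − 2^(−6/D)) / 6.
- Post-AA velocity: 0.9 / W. Post-AA doubling time by the 9.5 formula: W × ln2 / ln10.

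**Step 1: no effect, D unchanged.** The post-AA velocity is then (0.9/ln10) × ln2/D = 0.391 × ln2/D.
- Short gap: the after/before ratio is 0.391/P, which is 0.195 at P = 2 and 0.078 at P = 5. The falls are 80% and 92%.
- Six-month gap, P = 2: at D = 3, 0.250 to 0.090 per month, a 64% fall; at D = 10, 0.113 to 0.027, a 76% fall.
- Six-month gap, P = 5, D = 3: 0.625 to 0.090, an 86% fall.

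**Step 2: recovery at the plan's own timing, W = 3.** Post-AA velocity is 0.9/3 = 0.30 per month; post-AA doubling time is 3 × 0.693/2.303 = 0.90 months.

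| Entry PSA, D | Velocity before, short gap | Velocity before, 6-month gap | Velocity after | Doubling time |
|---|---|---|---|---|
| 5, 6 months | 0.578 | 0.417 | 0.30 (falls 48% or 28%) | 6 to 0.9 |
| 2, 3 months | 0.462 | 0.250 | 0.30 (falls or rises) | 3 to 0.9 |
| 2, 10 months | 0.139 | 0.113 | 0.30 (rises) | 10 to 0.9 |

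The first man improves on velocity and worsens on doubling time. For the second, the direction of the velocity change depends on how far apart his entry samples were. The third worsens on both.

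**Step 3: where the two measures disagree (W = 3).** With a short gap, P must exceed 0.30 × D/ln2: 1.3, 2.6 and 4.3 ng/mL at D = 3, 6 and 10. With a 6-month gap, P must exceed 1.8/(1 − 2^(−6/D)): 2.4, 3.6 and 5.3.

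**Step 4: how common this could be.** The documents give no entry distributions. With assumed uniform PSA (2-4, 2-6 or 2-10) and uniform D (2-12 months), short-gap velocity disagrees with doubling time in 26-93% of men for W = 2 to 4, and in 4-26% if W = 1. A longer sampling gap lowers these shares.

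**Step 5: would a log scale alone cure it?** No. With W = 2 to 4, post-AA doubling time is 0.6 to 1.2 months. Any man entering with a doubling time above about 1.2 months therefore appears to worsen before to after, even on AA alone, because PSA rebounds as castration wears off.

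**Step 6: windows just before course 2.** Here the window before and the window after both cover about 0.1 to 1.0. Velocity is 0.9/W and doubling time is 0.301 × W, so the two must agree and the level artefact does not arise.

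**The case against.** The best defence is that the plan reports two complementary descriptive measures in 12 men, with no test or decision attached. Much of that stands. A reader might infer that the sections swap one metric for another; they do not. Section 8.3 names slope and PSADT together, Section 9.5 lists both velocity and doubling time, and the word absolute is not used of velocity in 1.2 or 8.1.

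A reader might also infer that the before and after windows never share a PSA range. That fails too. Only the latest entry value must reach 2.0: a man at 2.0 with a 3-month doubling time was at 0.5 six months earlier. The rise before course 2 lies in the same band as the rise after it. The remark about values below 1.0 sits in the progression paragraph of 8.3 and does not limit the slope comparison.

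The short-gap figures are the upper end, and the no-effect falls in Step 1 and the fast recovery in Step 2 are separate scenarios that must not be combined.

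What does not stand is the claim that only detail is missing. Velocity change is a named secondary efficacy objective, and 8.3 intends to read slope change as a possible disease effect. Carried out as written against entry PSA, it gives a level-driven answer.

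**Conclusion.** The point holds for comparisons against entry PSA, on the usual reading of velocity as ng/mL per unit time. At an unchanged doubling time of 3 to 10 months, velocity falls by about 64-80% at PSA 2 and by up to 92% at PSA 5 with no vaccine effect. Under the assumed 3-month rise, velocity and doubling time can disagree outright: 28-48% better against 6 months shortening to 0.9.

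Two stronger conclusions are tempting and unsupported. One is that most men, or every man with a 3-month doubling time, would show the contradiction. The share depends on entry PSA, entry doubling time, sampling gap and speed of rise. With a 6-month gap, the 3-month threshold of 2.4 lies above the entry floor of 2.0. The other is that the efficacy conclusion of the trial is at risk. The primary endpoint is the within-subject difference in time to PSA progression; neither it nor its stated 98% power uses PSA velocity. This is a secondary-endpoint defect that should be corrected before analysis.

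**What to change.** - In 1.2, 8.1, 8.3 and 9.5, define the PSA-kinetics endpoint as the within-subject difference in log-PSA slope, using the regression in 9.5, between the AA+DC1 course and the AA-alone course, over the same post-AA PSA band up to 1.0 ng/mL. State the lower limit of the band. Both courses then share the PSA range and the rebound, and the randomised order balances the second-course delay expected in Section 5.
- Report any before-versus-after velocity or slope as descriptive only, with its formula and sampling windows, and not as evidence of a vaccine effect.
- Give the endpoint one status, secondary or exploratory, in every section.
- Correct the direction of benefit in 8.3: a lower slope or a longer PSADT is favourable.

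The cost is wording in four sections. No new samples are needed, since 9.5 already requires monthly PSA after each course. The before-to-after velocity figure loses its efficacy role. The new measure partly overlaps the primary endpoint, because over a fixed band the log slope also depends on how long the rise takes.

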2 BACKGROUND AND RATIONALE

2.1 Prostate Cancer

In 2007, approximately 225,000 new patients will be diagnosed with prostate cancer (PCa) in the US, and about 31,000 will succumb to the disease (most from metastatic disease) (Jemal et al., 2005). Standard treatment of organ-confined PCa includes surgery or radiation therapy, and is effective in the short term, but up to one third of patients relapse. Current systemic therapy (androgen ablation and chemotherapy) for PCa is limited, primarily palliative, and is associated with significant morbidity (Vogelzang, 1997). Most patients with advanced disease are treated with hormonal therapy and/or chemotherapy, and go on to develop resistance to both these modalities (DiPaola, 1999; Tannock et al., 2004). Prostate-specific vaccine therapy, if effective and if initiated early, i.e., at the time of initial relapse, offers the prospect of prolonging survival with minimal morbidity. Thus, we have chosen to focus on men with PCa, with a PSA relapse after either surgery and/or radiation therapy (Catalona and Smith, 1998; Dilliogluligil et al., 1997; Roach et al., 1999). This population of patients has less tumor burden, less molecular mechanisms of drug resistance, and may be more likely to respond to immune approaches to therapy (Blades et al., 1995; Sanda et al., 1995). Men with PSA-only disease also represent the largest sub-population of patients with PCa, for whom there is no standard treatment. Furthermore, they represent a heterogeneous group, with widely varying PSA-doubling times (Bubley et al., 1999; Pound et al., 1999).

2.2 PSA Progression after Local Therapy

Patients with PSA progression after local therapy represent an ideal population for the study of novel immune approaches. Current therapy for patients with PSA progression after local therapy is unclear, and a subset of patients can be selected with greater likelihood of progression to metastatic disease, supporting the need for novel approaches. Based on recent literature, men with a PSA-doubling time (PSA-DT) of less than 10 months are at the highest risk of rapid progression and are often offered androgen ablation therapy, either on an intermittent or a continuous schedule (Gulley et al., 2005; Pound et al., 1999). However, studies have not been completed to determine a benefit of early androgen ablation therapy in patients with PSA progression after local therapy (Gulley et al., 2005). Prior studies of adjuvant androgen ablation therapy have demonstrated a benefit in only select populations of patients (Hanks et al., 2003; Lawton et al., 2001; Messing et al., 1999). Two studies demonstrated a survival benefit of adjuvant androgen ablation in concert with definitive radiation therapy in patients with locally advanced prostate cancer (Hanks et al., 2003; Lawton et al., 2001). Another study demonstrated a survival benefit to androgen ablation therapy for stage D1 disease after surgery (Messing et al., 1999).

Predictive factors for a high risk of PSA-recurrence after local therapy have also been identified. Thus Pound et al. demonstrated that time to biochemical progression, Gleason score, and PSA

doubling time were predictive of the probability and time to the development of metastatic disease (Pound et al., 1999). Recently, D'Amico et al. also demonstrated the predictive value of PSA-DT, both pre-operatively as well as after definitive local therapy (D'Amico et al., 2004). These data support using Gleason score and PSA-DT as entry criteria to select and stratify patients at high risk of disease recurrence for novel approaches to systemic therapy.

Our target population for treatment will be men with prostate cancer, who have relapsed following surgery and/or radiation, and now have a rising PSA with a PSA doubling time (PSA-DT) of less than 10 months. This patient population is ideal for an immunologic intervention given that: i) this is the largest sub-population of men with prostate cancer in the U.S.; ii) there is no standard treatment for this sub-group; and iii) this sub-group has minimal systemic disease burden. We will carefully monitor immunological responses to vaccination at different time points, but the primary endpoint of vaccine efficacy will be time to PSA progression and stabilization of PSA levels. Several recent vaccine studies have validated failure of PSA progression as a good surrogate endpoint for lack of progression in clinical trials in prostate cancer (Bubley et al., 1999; Kelly et al., 1993; Scher et al., 2004).

